9.2.2 Data Selection for Multiple Results

Double-Blind Treatment Phase: For post-baseline assessments, if there are multiple non-missing results within the same analysis windows (including scheduled and unscheduled results) the non-missing result that is the closest to the target date will be used in the analyses; if more than one result is equally close, the result that is after the target date for the assessment will be used. If necessary, time of the assessments (if collected) will be used to determine the record to be selected. If there is still more than one result to be selected (but with different results), the average will be derived and then selected for analysis.

OLE Phase: The assessments performed at the nominal visits will be used in the analyses/summaries. Unscheduled assessments will only be used to determine worst, lowest and/or highest results post-baseline (where applicable).

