4.4. Patient Withdrawal and Follow-up

4.4.1. Patient Withdrawal

Patients are free to withdraw from the study at any time for any reason. A patient may also be withdrawn from the study by the Investigator or the Sponsor at any time for safety, behavioral, or administrative reasons if either determines that it is not in the patient's best interest to continue participation.

Possible reasons for early withdrawal include:

- AE
- Lack of effect
- Patient/parent(s)/legal guardian(s) decision
- Lost to follow-up
- No longer meets eligibility criteria
- Non-compliance with study protocol
- Non-compliance with study drug treatment
- Other, with specific reason (e.g., pregnancy)

Patients who develop end-stage renal disease (eGFR of <15 mL/minute/1.73 m²), severe hepatic impairment (Child-Pugh C), or any other medical condition that in the opinion of the Investigator may pose a risk to the patient must be discontinued from the study.

The following ECG findings, based on the mean of triplicate 12-lead ECGs, require discontinuation from the study:

- Mean QTcF >500 ms
- Mean QTcF increase from Screening >60 ms AND mean QTcF >470 ms
- Heart rate increase from Baseline >65% or decrease from Baseline >40%

Any patient with a new positive response on question 4 (active suicidal ideation with some intent to act, without specific plan) and/or question 5 (active suicidal ideation with specific plan and intent) of the Very Young Child/Cognitively Impaired-Since Last Contact C-SSRS (Appendix M) will be discontinued and will require further evaluation by the Investigator.

The date and primary reason for early withdrawal will be recorded in the electronic case report form (eCRF). At the time of withdrawal from the study, every attempt should be made to complete the Early Termination (ET) Visit assessments (Section 7.3.3 and Section 7.4.3).

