9.2.1 Visit Window

The visit window and PK draw window appear in Table 5 and Table 6, respectively. For the Double-Blind Treatment Phase, unless otherwise stated, the endpoints will be analyzed and reported using the analysis visits as determined by the windowing. For the OLE Phase, unless otherwise stated, the nominal visit will be used.

During the Double-Blind Treatment Phase, if a patient stopped taking treatment before their CRF Visit 3 (start of the stable dose) for a reason other than AE and then re-started study treatment more than 14 days after the treatment interruption, the analysis visit window for post-baseline visits will be derived using (as Day 1) the date the patient re-started their study treatment (i.e., the visit window will not be based on date of first dose for that patient).

Table 5: Visit Window and Target Day

Phase	Protocol Visit	Analysis Visit	Target Day	Visit Window Lower Limit	Visit Window Upper Limit
Safety: Vital Signs (including Height and Weight), Physical Examination, Clinical Laboratory, 12-lead ECG Efficacy: ESS-CHAD (parent/caregiver version), CaGI-S, CGI-S					
Screening	Visit 1 Visit 2	Baseline	-1	- inf	1
	Visit 3	Visit 3 (Day 22)	22	2	35
Daubla	Visit 4	Visit 4 (Day 50)	50	36	63
Double- Blind	Visit 5	Visit 5 (Day 77)	77	64	Treatment Phase Completion ^a
OLE	Visit 6	Visit 6 (Month 4)	99		-
	Visit 7	Visit 7 (Month 6)	189		

Dhasa	Protocol	Analysis Visit	Tayget Day	Visit Window	Visit Window
Phase	Visit		Target Day	Lower Limit	Upper Limit
	Visit 8	Visit 8 (Month 9)	279		
	Visit 9	Visit 9 (Month 12)	369		
Visit x		Visit x (Month y) ^b	Previous visit target day + 180		
Efficacy: G	hrelin meas	urements			
Screening	Visit 2	Baseline	-1	- inf	1
Double- Blind	Visit 5	Visit 5 (Day 77)	77	2	+ inf
Efficacy: C	ogstate		-		•
Screening	Visit 1	Baseline	-1	- inf	1
Screening	Visit 2	Dascinic		- 1111	
	Visit 4	Visit 4 (Day 50)	50	36	63
Double- Blind	Visit 5	Visit 5 (Day 77)	77	64	Treatment Phase Completion ^a
	Visit 6	Visit 6 (Month 4) ^c	99		
OL E	Visit 7	Visit 7 (Month 6)	189		
OLE	Visit 8	Visit 8 (Month 9)	279		
	Visit 9	Visit 9 (Month 12)	369		
Efficacy: A	BC-2, MER	S-PWS ^c , ZBI-22, HQ-0	CT and FSZQ		
Screening	Visit 1 Visit 2	Baseline	-1	- inf	1
	Visit 3	Visit 3 (Day 22)	22	2	35
	Visit 4	Visit 4 (Day 50)	50	36	63
Double- Blind	Visit 5	Visit 5 (Day 77)	77	64	Treatment Phase Completion
OLE	Visit 6	Visit 6 (Month 4)	99		
	Visit 7	Visit 7 (Month 6)	189		
OLE	Visit 8	Visit 8 (Month 9)	279		
	Visit 9	Visit 9 (Month 12)	369		
PK					

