Discontinued	Present	Present	Missing	Missing data after the discontinuation will be imputed within treatment group using MI approach with observed values at all available time points (including Baseline).	
due to any reason but lack of efficacy or	Present	Missing	Missing		
AE	Missing	Missing	Missing		

Abbreviations: AE = Adverse Event; MI = Multiple Imputation.

Note: Multiple imputation method is performed using the analysis visits, i.e., if the nominal result is missing, and there is an unscheduled result or if the ET result falls within the visit window that assessment will be used at that visit.

Step 1. Monotone Missing Pattern: Intermittent missing data will be imputed within treatment group using MI under a missing at random assumption with observed values at all available time points (including Baseline).

- a. From the analysis dataset containing the ESS-CHAD (parent/caregiver version) results, select all the patients (regardless of the discontinuation reason and status). The dataset will contain indicators variables for subject ID: SUBJID, planned treatment: TRTP, Baseline results: BASELINE, Visit 3 results: VISIT3, Visit 4 results: VISIT4 and Visit 5 results: VISIT5) and there will be one record per patient. Before transposing the dataset to get the required structure, if there are multiple non-missing records for a patient, select the record to include as per the rules defined in section 9.2.
- b. Using this dataset with treatment as covariate, imputed datasets (called imputations) will be produced using the Markov Chain Monte Carlo (MCMC) method implemented with the SAS MI procedure. The imputed datasets will contain the observed value (where it was not originally missing) or imputed values as per the model (for missing observations). The values imputed by MCMC method for the missing values will be used for patients who completed the treatment phase but have monotone patterns of missing data.

Step 2. Missing data for patients who discontinued for other reasons (i.e., not due to lack of efficacy or AE): Missing data after the treatment discontinuation (i.e., in the 'tail' end) will be imputed within treatment group distribution (intermittent missing data will have been imputed at the previous step). Patients who completed the treatment but have missing values not imputed at the previous step (i.e., at the 'tail' end) will have their missing imputed together with patients who discontinued for other reasons.

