12.6.6 Electrocardiograms

Triplicate 12-lead electrocardiogram (ECG) will be obtained after the patient has been resting for at least 5 minutes. For clinically significant ECG findings, a follow-up ECG should be performed within 24 hours and again 7 days later to ensure the abnormality is not worsening. Follow-up 12-lead ECGs may be performed locally, with the results sent to the Investigator.

Heart rate, PR interval, RR interval, QRS duration, QT interval, QTcB interval, QTcF interval as well as investigator's interpretation of the ECG will be collected in the eCRF. All ECG results along with the investigator's interpretation, including the average of triplicate measurements at each timepoint, will be presented in data listings.

QTcF values will be presented with the implementation of corrections (i.e., Fridericia's) as defined in International Council for Harmonisation (ICH) Guidelines E14. Frequency count and percentage will be tabulated by the following categories. This summary will also be provided for each of age groups (6 to <10 years; 10 to <20 years and 20 to ≤65 years) and sex for the Double-Blind Treatment Phase. The same summaries by age groups and/or sex may be repeated for the OLE Phase.

Absolute QT interval corrected for heart rate based on Fridericia's formula (QTcF) prolongation:

- QTcF interval >442 ms (6 to <10 years old)
- QTcF interval >439 ms (10 to <20 years old)
- QTcF interval >450 ms (male, 20 to ≤65 years)
- QTcF interval >470 ms (female, 20 to \leq 65 years)
- QTcF interval >500 ms (regardless of age and gender)

Change from Baseline in QTcF interval:

- QTcF interval increases from Baseline 30-60 ms
- QTcF interval increases from Baseline >60 ms

In addition, potential QT prolongations will be categorized as:

- PR interval >300 msec
- QRS duration >140 msec
- PR interval increase from Baseline >50%
- QRS duration increase from Baseline >40%
- HR increase >65% from Baseline
- HR decrease >40% from Baseline

The actual values and change from Baseline values at each time point will be summarized for the safety populations. The overall interpretation will also be summarized by timepoint as well as the worst post-baseline.

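### SAP 12.6.6 does not say that the double-blind ECG outlier categories count any post-baseline ECG, so the one-result-per-window rule in SAP 9.2.2 can leave out an ECG that crossed a threshold.

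*SAP*

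**What the plan says.** **Windows.** SAP 9.2.1 makes windowing the default for the double-blind phase: unless otherwise stated, "the endpoints will be analyzed and reported using the analysis visits as determined by the windowing". The first block of Table 5 covers "Safety: Vital Signs (including Height and Weight), Physical Examination, Clinical Laboratory, 12-lead ECG", together with three efficacy scales. The windows are Days 2–35 (target Day 22), Days 36–63 (target Day 50), and Day 64 to completion of the phase (target Day 77).

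**Selection.** Under SAP 9.2.2, when a double-blind window holds several results, scheduled or unscheduled, "the non-missing result that is the closest to the target date will be used in the analyses". A tie goes to the result after the target. The OLE has its own paragraph: nominal visits are summarised, and unscheduled results serve to find worst, lowest or highest post-baseline values. The double-blind paragraph has no such provision.

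**ECG categories.** SAP 12.6.6 asks for counts and percentages by age- and sex-specific QTcF limits, QTcF above 500 ms, rises of 30–60 ms, "QTcF interval increases from Baseline >60 ms", and PR, QRS and heart-rate limits. It does not say whether a patient is counted per visit or at any time. Worst post-baseline is specified for the overall ECG interpretation only.

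**Stopping criteria.** Protocol 4.4.1 requires discontinuation for mean QTcF above 500 ms, for "Mean QTcF increase from Screening >60 ms AND mean QTcF >470 ms", and for heart-rate changes beyond stated percentages. The ET visit repeats the Visit 5 assessments, triplicate ECG included (Protocol 7.3.3).

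**The concern.** An outlier table exists to show whether a patient ever crossed a limit. Selecting the value nearest a target day answers a different question, and it works against ECGs recorded away from schedule, which is when an unexpected finding is likely to be followed up. Stopping treatment also generates a second ECG, at the ET visit, which can displace the one that led to the stop.

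This matters because safety is part of the primary objective (Protocol 2.1) and Protocol 1.4 states that the drug prolongs the QT interval. QTcF above 500 ms and the heart-rate changes are both discontinuation criteria and SAP categories, so the patients who could be missed include those the protocol requires to be stopped.

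**Working it through.** The plan states no figure on this point to reproduce. The check applies the SAP's own rule to possible ECG days.

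**Inputs.** Windows and targets: SAP Table 5. Selection: SAP 9.2.2, smallest |day − target|, ties to the later day. Visit tolerance: ±3 days. Arm size: 20 (Protocol 9.2). QTcF values are illustrative.

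**1. Unscheduled ECG, then ET.** Unscheduled ECG on Day 40, mean QTcF 505 ms; ET ECG on Day 43, 450 ms. Both fall in Days 36–63.
- |40 − 50| = 10
- |43 − 50| = 7, so Day 43 is selected.

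The patient met the 500 ms criterion but is not counted above 500 ms.

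**2. Scheduled ECG on target.** Visit 3 on Day 22 and an unscheduled or ET ECG on Day 30: |22 − 22| = 0 against |30 − 22| = 8, so Day 30 is dropped. When the scheduled ECG is on target, every ECG on another day of that window is dropped. After Visit 3 on Day 22 that means Days 23–35 (13 days); after Visit 4 on Day 50, Days 51–63 (13 days).

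**3. Scheduled ECG off target.**

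| Visit 3 day | Later ECG dropped on | Later ECG replaces the visit on |
|---|---|---|
| 19 | Days 26–35 (10 days) | Days 20–25 |
| 22 | Days 23–35 (13 days) | none |
| 25 | Days 26–35 (10 days) | none |

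So a threshold ECG at a scheduled visit can also be lost. If Visit 4 is on Day 47, an ET ECG on any of Days 48–53 replaces it (Day 53 ties at 3 days and wins as the later result). A threshold ECG at a scheduled visit on or after its target day is kept against later ECGs in the window.

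**4. Size.** 1/20 = 5 percentage points of an arm, and 1/40 = 2.5 of the pooled active group.

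**5. Neighbouring rules in the SAP.**

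| Item | Stated basis |
|---|---|
| Laboratory shifts (12.6.3) | lowest and highest post-baseline |
| Overall ECG interpretation (12.6.6) | each timepoint and worst post-baseline |
| Unscheduled results, OLE (9.2.2) | worst, lowest or highest, where applicable |
| Vital-sign categories (12.6.4) | each visit |
| QTcF, PR, QRS, heart-rate categories (12.6.6) | none |

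With nothing stated in 12.6.6, the 9.2.1 default and the 9.2.2 selection apply.

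**The case against.** The best defence is that SAP 12.6.6 never says these categories are by visit. Vital-sign categories are explicitly per visit and the QTcF sentence is not, so a programmer could take worst values. The table shells are a separate document (SAP 12.0) and may settle it. There are also backstops: every ECG and its triplicate average is listed, clinically significant ECG findings must be recorded as adverse events (Protocol 6.5.1 and 8.1.1), and events leading to discontinuation of study drug are tabulated. With about 60 patients, a QTcF stop would remain visible. Unscheduled double-blind ECGs are discretionary (Protocol 7.6).

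Most of this stands, and it limits the point: the loss is possible rather than certain, and it affects a summary table rather than the record. It does not remove the point, because the worst-value reading is not written and the written default points the other way. A listing does not correct an outlier count that reads zero.

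Two stronger readings are tempting.

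*The same rule damages the primary analysis.* A reader might infer this because an ET ESS-CHAD score can be discarded when a scheduled score is nearer the target; the SAP Table 7 note lets an ET score stand in where the nominal one is missing. The documents do not support a change. Either choice discards one observed score. Simulation under assumed inputs (SD 5, correlations 0.6–0.8, 5–15% of an arm stopping) cuts both ways. If stopping follows the later score, using the ET score reduces bias in that arm's mean by 0.05 to 0.11 points (0.13 to 0.08; 0.51 to 0.40). If stopping follows the scheduled score, the present rule is biased by at most 0.01 and the switch introduces 0.07 to 0.21. SAP 12.4.1.3.2 also rules out special handling for patients who discontinue, and the discarded scores precede Day 64, so they are not Week 11 data.

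*The compound stopping criterion is wrongly omitted.* A reader might infer an error because no category reproduces the rise from Screening above 60 ms with QTcF above 470 ms. But a discontinuation criterion need not be a summary category, and SAP 12.6.6 carries every QTcF category in Protocol 9.4.3. A 15-year-old at 405 ms (Screening), 415 ms (Baseline) and 472 ms on treatment meets the criterion (472 − 405 = 67) and is tabulated as a 30–60 ms rise (472 − 415 = 57), but is also counted above 439 ms.

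**Conclusion.** The point holds for the double-blind ECG categories. Followed as written, SAP 9.2.1, 9.2.2 and 12.6.6 allow an unscheduled, ET or early scheduled ECG beyond a limit to be left out of the QTcF, PR, QRS and heart-rate counts. Each patient missed is 5 percentage points of an arm of 20.

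This rests on three conditions: two or more ECGs share a window, the one beyond the limit is not selected, and the table shells do not already specify any-time counting. How often the first two will occur cannot be estimated from the documents. Protocol 6.5.4 places repeat ECGs at 24 hours and 7 days in the OLE, whereas SAP 12.6.6 sets no phase limit; the unscheduled and ET cases above do not depend on how that is read.

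The conclusion does not extend to the ESS-CHAD analysis. The compound criterion is an optional addition, not a correction. No view is taken on the clinical thresholds.

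**What to change.** In SAP 12.6.6, state that the QTcF, PR, QRS and heart-rate categories are counted on any post-baseline double-blind ECG, using triplicate means and including unscheduled and ET ECGs, alongside any by-visit table. This brings them into line with the laboratory shifts and the OLE rule.

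Optionally, add a descriptive count of patients meeting the Protocol 4.4.1 compound criterion exactly as that section states it, since SAP 12.6.6 measures rises from Baseline only.

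Leave the ESS-CHAD selection rule in SAP 9.2.2 unchanged.

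The cost is one sentence of SAP wording and one additional safety table, or an extra row block in the existing one. No new data are needed, and the by-visit summaries and efficacy analyses are unaffected.

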9.3 Baseline

For the Double-Blind Treatment Phase, Baseline is defined as the last record or measure collected prior to the study drug administration. For the OLE Phase, Baseline will be identical to the Double-Blind Treatment Phase, i.e., the last non-missing record or measure collected prior to study drug administration.

9.4 Date of Last Dose

For patients who are lost to follow-up and for which the date of last dose was not known, the date of last dose will be imputed by the date the patient was lost to follow-up, i.e. the date of the Double-Blind Treatment Phase Completion/Discontinuation as collected in the CRF. The imputed date of last dose will be used in the determination of TEAEs, concomitant medications, and duration of exposure.

^a In the Double-Blind Treatment Phase, if the patient did not enter the OLE Phase, the upper limit of the visit window should be the date of the end of the completion of the treatment phase as collection in the CRF; if the patient entered the OLE Phase, the upper limit of the visit window should be the first dose of study drug intake in the OLE

^b Patients will have on-site visits every 6 months (months 18, 24 etc.). Target day is derived by adding 180 days to the previous visit target day.

^cNot collected at Visit 6 (Month 4) in protocol version 6 and subsequent protocol version(s).

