4.4.5. Patients Deemed Lost to Follow-up

Investigators should make every effort to contact patients/parent(s)/legal guardian(s) who are potentially lost to follow-up, including pursuing any alternative contact methods permitted by local regulations or agreed by the patient/parent(s)/legal guardian(s). All attempts to contact the patient/parent(s)/legal guardian(s) will be documented in the patient's eCRF and source notes. At a minimum, three documented attempts to contact the patient/parent(s)/legal guardian(s), including at least one certified letter, should be performed before a patient is deemed lost to follow-up.

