12.3.2.1 Double-Blind Treatment Phase

The duration of exposure to study drug, number of days with intake of study drug and compliance (during the stable dose period) with study drug dosing will be summarized for the Double-Blind safety population. In addition, the number of tablets taken (i.e., returned – dispensed) will be listed for the titration phase and the stable dose phase in the Double-Blind Treatment Phase.

Study drug accountability including bottle number and number of dispensed and returned tablets will be listed. Study drug not returned will be assumed to have been taken.

Percentage of patients meeting study drug compliance during the stable-dose period will be presented in the following categories: <80%, $\ge80\%$ to $\le120\%$, and >120%. Major non-compliance is defined as compliance <80% or compliance >120%.

Duration of exposure: Date of last dose in the Double-Blind Treatment Phase – date of first dose in the Double-Blind Treatment Phase + 1

Number of days with at least one dose (tablet) taken: Duration of exposure in the Double-Blind Treatment Phase – number of days with missed doses in the Double-Blind Treatment Phase

Study drug compliance (stable-dose period): The start date of the stable dose period is the date of Visit 3 (Day 22) and the end of the stable dose period is the last dose date in the Double-Blind Treatment Phase; during that period patients ages 6 to <12 years should take 4 tablets daily, patients ages 12 to <18 years should take 6 tablets daily, and patients ages \ge 18 years should take 2 tablets daily; i.e., compliance is the number of tablets taken during that period (i.e., sum of the tablets dispensed minus the sum of the tablets returned) divided by (x times the number of days in the period [date of last dose – dispensed date at Visit 3 +1]), where x is 4 for patients ages 6 to <12 years, 6 for patients ages 12 to <18 years and 2 for patients ages \ge 18 years.

The data from the dose-escalation period was not included in the derivation of the compliance as the dates when the patient dose-escalated to the next dose level is not collected in the eCRF and the number of tablets to be taken at each dose level is different.

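### Imputed exposure for lost patients is not capped at the tablets supplied, and unreturned bottles put some early stoppers above 120% compliance

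*SAP*

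**What the plan says.** SAP 9.4 gives one rule for a missing last-dose date. Its trigger is narrow: "For patients who are lost to follow-up and for which the date of last dose was not known". In that case "the date of last dose will be imputed by the date the patient was lost to follow-up", which the section equates with the date of "Double-Blind Treatment Phase Completion/Discontinuation as collected in the CRF". The imputed date "will be used in the determination of TEAEs, concomitant medications, and duration of exposure". Compliance is not on that list.

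SAP 12.3.2.1 defines duration of exposure as "Date of last dose in the Double-Blind Treatment Phase – date of first dose in the Double-Blind Treatment Phase + 1". It also says: "Study drug not returned will be assumed to have been taken". Stable-dose compliance is tablets dispensed minus tablets returned, divided by x times the number of days. The days are "date of last dose – dispensed date at Visit 3 +1", and x is 4, 6 or 2 for children, adolescents and adults. Results below 80% or above 120% are major non-compliance.

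Under Protocol 4.4.5, a minimum of three documented contact attempts, "including at least one certified letter, should be performed before a patient is deemed lost to follow-up". Protocol 5.5 asks for all bottles back at each on-site visit.

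The available text of these sections neither limits an imputed last dose to the supply in hand nor makes an exception for bottles that never come back.

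**The concern.** Two separate rules can misfire.

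- **Exposure.** The date on which a patient is declared lost follows the contact attempts, so it is later than the last contact. Using it as the last dose credits daily dosing through a period nobody observed. If the date falls after the tablets would have run out, the recorded duration cannot be true.
- **Compliance.** If a patient stops early on a known date and keeps the bottles, the numerator counts every tablet dispensed while the denominator counts only the days up to the stop. The ratio then measures bottle return, not dosing, yet the patient is tabulated as majorly non-compliant on the high side.

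At stake is how well the exposure and compliance tables describe the patients who left early. Safety is part of the primary objective, so those tables give the context for reading the adverse events.

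**Working it through.** **Inputs.** Tablet strengths: Protocol 5.1.1. Higher doses: Protocol Table 7. Kit contents: Protocol 5.2.1. Formulas and limits: SAP 12.3.2.1. Visits are taken on their target days (Visit 3 on Day 22, Visit 4 on Day 50) and the first dose on Day 1.

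**1. Reproduce the SAP's tablets per day.** Dose divided by tablet strength: 17.8/4.45 = 4; 26.7/4.45 = 6; 35.6/17.8 = 2. These match the SAP.

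**2. Supply per stable-dose box.** Tablets divided by x: children 4 × 30 / 4 = 30 days; adolescents 6 × 30 / 6 = 30 days; adults 2 × 30 / 2 = 30 days. The box is meant for 28 days. Because every age group gets 30 days, the results below do not depend on age.

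**3. Last day the supply can cover.** Titration bottles hold 10 days' tablets for each of the three weekly steps, so a patient supplied only at Baseline is covered to Day 30. Supplied at Visit 3: 22 + 30 − 1 = Day 51. Supplied at Visit 4: 50 + 30 − 1 = Day 79. If every spare tablet was kept and used, the limits are Days 30, 60 and 90.

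**4. Imputed duration against supply.** Duration = lost date − first dose + 1.

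| Last supplied | Declared lost | Imputed duration (days) | Supply covers to | Excess (days) | Excess if all spares kept (days) |
|---|---|---|---|---|---|
| Baseline | Day 77 | 77 | Day 30 | 47 | 47 |
| Visit 3 | Day 50 | 50 | Day 51 | 0 | 0 |
| Visit 3 | Day 77 | 77 | Day 51 | 26 | 17 |
| Visit 4 | Day 77 | 77 | Day 79 | 0 | 0 |
| Visit 4 | Day 91 | 91 | Day 79 | 12 | 1 |

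The lost dates are illustrations. The documents do not say how long after last contact a patient is declared lost.

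**5. Compliance with a known stop and nothing returned (adult).** With d the days from Visit 3 to last dose inclusive, compliance is 60/(2d) with one box and 120/(2d) with two.

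- Stop 10 days after Visit 3, one box: d = 11, 60/22 = 273%.
- Above 120% with one box: 60/(2d) > 1.2, so d < 25, a last dose on Day 45 or earlier.
- Above 120% with both boxes: 120/(2d) > 1.2, so d < 50, a last dose on Day 70 or earlier.
- Completer on Day 77: d = 56, 120/112 = 107%.
- If the first of these patients returns the unused tablets, 22/22 = 100%. The formula works when bottles come back.

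**6. Compliance if an imputed date were used.** Last supplied at Visit 3, nothing returned, last dose imputed as Day 77: 60/(2 × 56) = 53.6%. A late imputed date lowers compliance, the opposite direction from step 5. Because SAP 9.4 does not list compliance among the uses of the imputed date, this case is an inference from the denominator's wording.

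**The case against.** The strongest reply is that both rules are disclosed conventions with limited reach. The imputation applies only when the last-dose date is unknown. Early stoppers are required to complete an Early Termination visit with drug accountability (Protocol 4.4.3 and 7.3.3), so keeping every bottle should be the exception. Dispensed and returned counts are listed, so non-return is visible. The SAP calls a result above 120% major non-compliance, not overdosing. All of this stands and limits how often the rules misfire. It does not make their output right when they do.

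Several stronger readings are tempting, but the documents do not support them:

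- *Every lost patient gets impossible exposure.* This needs both an unknown last dose and a lost date beyond the supply. Two of the five rows in the table show no excess.
- *A patient lost in the open-label extension gets a last dose before the first open-label dose.* SAP 9.4 equates the date of loss with the double-blind completion or discontinuation date, which makes sense only for losses in that phase. The fair reading is that no rule is given for the extension. The gap affects extension duration and planned average daily dose (SAP 12.3.2.2). It does not affect which extension events and medications are reported, because those are selected from the first open-label dose (SAP 9.6 and 12.6.1).
- *Lost patients appear as over-dosers.* The figures above 120% come from the unreturned-drug rule combined with an early stop date. A late imputed date pushes compliance down.
- *Loss to follow-up will be the commonest exit from the extension.* Protocol 4.4.1 lists it among several reasons and gives no frequencies.

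A short stretch of SAP text directly after the double-blind compliance rules was not available, so an exception there cannot be excluded.

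**Conclusion.** The point holds in a limited form, at minor severity. As written, imputed double-blind exposure can exceed the drug supplied: by 26 days for a patient last supplied at Visit 3 and declared lost on Day 77 (17 if every spare tablet was kept), and by none if supplied at Visit 4. Separately, a patient with a known early stop who returns nothing is classed above 120% if the stop falls fewer than 25 days into the first stable-dose box, or fewer than 50 days into the period with both boxes kept.

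The exposure result rests on target-day visits and an assumed lost date. The compliance result is arithmetic on the SAP's own formula and needs only that no bottles come back. The number of patients affected cannot be derived from the documents. What suffers is mainly the descriptive exposure and compliance summaries. A later last dose lengthens the 30-day adverse-event window, but that errs on the cautious side. The primary repeated-measures model uses none of these quantities.

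**What to change.** 1. **SAP 9.4, for duration of exposure.** Impute the last dose as the earlier of (a) the CRF discontinuation date of the phase the patient was in, which means the extension's own date for extension patients, and (b) the last day covered by dispensed tablets, that is, dispensing date + tablets/x − 1 for the stable-dose boxes. State whether spare tablets from earlier boxes count. Flag imputed dates in the listing and give their number in the exposure table.
2. **SAP 9.4, for adverse events.** The treatment-emergent window may stay on the later date.
3. **SAP 12.3.2.1.** Where bottles are not returned, set tablet-count compliance to missing and show those patients in a separate not-returned category, neither above 120% nor below 80%. Use diary or missed-dose data only where they exist. A lost patient who keeps the bottles probably keeps the diary too.
4. **Same section, wording.** Tablets taken is once written as returned minus dispensed, the reverse of the compliance formula, and should be corrected.

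The cost is a few lines of SAP text, a second last-dose variable for the affected patients and one extra table row. The trade-off is that fewer patients have a numerical compliance value. Protocol 1.3.2 describes the double-blind phase as completed. If its tables already exist, the change there would be a documented supplementary table, while the extension rule can go into an SAP update before the extension database lock.
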